8.1.1 Study Schema

Figure 2: Study Schema

TC=telephone call

8.1.2 Schedule of Assessments

Table 1: Schedule of Assessments

RD.06.SPR.112199

RD.06.SPR.115230

Visit	1	2	2b ^{a,b}	3	4	4b ^{a,b}	5 ^{a,b}	6 ^{a,b}	1	2 (7)	TC	3 (8)
Purpose	Medical history and labs	First DL-PDT session	If required	Follow-up 1 week after 1 st DL-PDT	Second DL-PDT session	If required	Follow-up 1 week after 2 nd DL-PDT	Final 12 weeks after last DL-PDT	Visit 6 is Visit 1 of LTFU study	26 weeks after last DL-PDT	Telephone call to check on subject	Final 52 weeks after last DL-PDT
Week	Screening	Baseline			Week 2		Week 3	Week 14/ET ^c		Week 14 Week 28	Week 26 Week 40	Week 40/ET Week 54
Visit window	-14 to -5 days	0 to +14 days			0 to +14 days		-2 to +14 days	-2 to +28 days		+/- 5 days	+/- 5 days	+/- 5 days
LONG-TERM FOLLOW-UP STUDY												
Informed Consent CCI	X								X			
Demographics (including FST)	X								X			
Medical History	X								X			
Previous Therapies/Procedures	X								X			
Vital Signs/Physical Examination	X							X ^g →	X			
Inclusion/Exclusion Criteria	X	X						X →	X			
Hematology/ Blood Chemistry/ UA/ECG	X							X				
Pregnancy Test ^c	X	X	X		X	X		X →	X	X		X
Weather assessment		X	X		X	X						
CCI												
AK mapping + counting + grading ^d		X	X		X	X		X →	X	X		X
Sunscreen application		X	X		X	X						

Visit	1	2	2b ^{a,b}	3	4	4b ^{a,b}	5 ^{a,b}	6 ^{a,b}	1	2 (7)	TC	3 (8)
Purpose	Medical history and labs	First DL-PDT session	If required	Follow-up 1 week after 1 st DL-PDT	Second DL-PDT session	If required	Follow-up 1 week after 2 nd DL-PDT	Final 12 weeks after last DL-PDT	Visit 6 is Visit 1 of LTFU study	26 weeks after last DL-PDT	Telephone call to check on subject	Final 52 weeks after last DL-PDT
Week	Screening	Baseline			Week 2		Week 3	Week 14/ET ^c		Week 14 Week 28	Week 26 Week 40	Week 40/ET Week 54
Visit window	-14 to -5 days	0 to +14 days			0 to +14 days		-2 to +14 days	-2 to +28 days		+/- 5 days	+/- 5 days	+/- 5 days
Lesion débridement and treatment application		X	X		X	X						
Geolocalized Satellite data and exposure time		X	X		X	X						
Study drug(s) Dispensing (D) and Accountability (A)		X	X		X	X						
Subject Assessment of Pain		X	X		X	X						
Subject Skin Aspect Assessment ^d								X				
Subject satisfaction questionnaire ^d					X	X		X ^d				
Safety Visit Question				X			X					
Adverse Events ^e	X	X	X	X	X	X	X	X [→]	X	X	X	X
Concomitant Therapies/Procedures ^d		X	X	X	X	X	X	X [→]	X	X	X	X
Subjects with Complete Response evaluation and IC for continuation into long-term follow-up study								X				
Exit form ^f								X				X

Visits 2 and 4 may be delayed for up to 2 weeks in case of unsuitable weather conditions at randomization/treatment outset; these visits will be Visits 2b and 4b. These postponements will be automatically added to the time of scheduled Visits 5 and 6

If subjects experience rain during the 2 hours of daylight exposure of either DL-PDT visit, they will be instructed to go indoors at the investigative site and the study drug will be washed off. The treatment will be considered incomplete and should be repeated at a minimum interval of 2 weeks. There will be only one attempt at retreatment of an incomplete treatment. These visits will be Visits 2b and 4b. If the attempt at retreatment is also incomplete, the subject will not be excluded from the study. Likewise, these repeat visits will be added to the time of scheduled Visits 5 and 6. If a subject has two incomplete visits in a row, the subject will continue with assessment in this study.

- a) Only for females of childbearing potential, UPT at Visits 1,2, and 3 of this study
- b) Should be performed earlier if subject discontinues before Visit 3 of this study
- c) Adverse Events have to be collected from the time of the Informed Consent signature
- d) Exit form should be completed after subject data collection has been completed for subjects in the study; FST=Fitzpatrick Skin Type
- e) Red arrows signify that pertinent data obtained at Visit 6 of RD.06.SPR.112199 will be transcribed as this visit as Visit 1 of RD.06.SPR.115230

8.2 Discussion of Study Design

8.2.1 Study Design

This study will evaluate recurrence of AKs treated in study RD.06.SPR.112199. In this study, investigators will review the condition of lesions mapped and treated in that study, over a 9-month follow-up. Only those subjects who achieve a Complete Response at the Final Visit from the vehicle and active cream groups in that study, are eligible to continue in this long-term follow-up study.

In study RD.06.SPR.112199, approximately 570 subjects with mild to moderate actinic keratoses of the face and scalp, meeting specific criteria, will receive 2 sessions of DL-PDT, randomized to receive either MAL 16.8% cream (CD06809-41) or vehicle cream in a **CCI** ratio. It is estimated that 380 subjects would receive MAL DL-PT and 190 subjects would receive vehicle cream DL-PDT at 2 treatment sessions 2 to 4 weeks apart. The endpoint of study RD.06.SPR.112199 occurs at Visit 6, 12 weeks after the last DL-PDT treatment, when the treated AK lesions are assessed for complete response. The subject complete response, defined as the proportion of subjects with complete clearance of all AK lesions treated, will compare MAL cream with vehicle cream. In the powering of the study, the assumptions of a 45% subject complete response for MAL 16.8% cream (CD06809-41) and 15% subject complete response for vehicle cream were used. Because there will be subjects enrolling in the long-term follow-up study from both treatment arms, it is essential to keep the subjects and the site personnel blinded to the treatment, in order to not bias the evaluations of recurrence scheduled at Visits 2 and 3 of this study, occurring 26 and 52 weeks after the last DL-PDT.

Approximately 130 subjects who completed the study RD.06.SPR.112199 and achieve complete response of all treated lesions (estimated to be 111 randomized to MAL DL-PDT and 19 randomized to Vehicle DL-PDT) will be enrolled in this study in order to have approximately 100 subjects randomized to MAL DL-PDT who complete the long-term follow-up.

8.3 Selection of the Study Population

8.3.1 Number of Planned Subjects

Approximately 130 subjects.

Refer to [Section 10.2](#) for the statistical considerations on which the sample size is based.

8.3.2 Inclusion Criteria

To be eligible for study entry, subjects must satisfy all of the following inclusion criteria:

1. Subjects who have participated in study RD.06.SPR.112199 and have achieved a complete response at Final Visit of that study, complete clearance of treated lesions at 12 weeks after the last DL-PDT.
2. Written Informed Consent before any assessment related to the LTFU study is performed.

3. Subject is willing and able to comply with all of the time commitments and procedural requirements of the clinical study protocol.

8.3.3 Exclusion Criteria

Subjects will be excluded from the study if 1 or more of the following criteria are applicable:

1. Subjects, who develop or experience a condition that may compromise subject safety or compliance, interfere with evaluation or preclude completion of the study. In particular, these conditions include, but are not limited to malignancy or other life threatening diseases.
2. Pertinent non-compliance with the conditions for this study or instructions by the investigator during RD.06.SPR.112199.

8.3.4 Removal of Subjects From Assessments

Although the importance of completing the entire clinical study will be explained to the subjects, any subject is free to discontinue his/her participation in the study at any time and for whatever reason, specified or unspecified, and without any prejudice. No constraints are to be imposed on the subject, and when appropriate, a subject may be treated with other conventional therapy when clinically indicated. Investigators or the Sponsor can also withdraw subjects from the clinical study if deemed to be necessary. Data collected up to the time of subject removal will be used.

Reasons for discontinuing the study include:

- WITHDRAWAL BY SUBJECT
Subject request (i.e., consent withdrawal)
- PROTOCOL VIOLATION
Use of non-permitted concurrent therapy (unless discussed and agreed upon with the Investigator and medical monitor) see [Section 8.3.7](#)
- NON-COMPLIANCE WITH STUDY SCHEDULE
- LOST TO FOLLOW-UP
- ADVERSE EVENT
Occurrence of AEs not compatible with the continuation of subject participation in the study, in the Investigator's opinion, or unacceptable to the subject to continue
- PHYSICIAN DECISION
- OTHER

The reason(s) for withdrawal will be documented in the eCRF.

Subjects who prematurely discontinue the study will be encouraged to complete the Final/ETstudy visit.

Reasonable efforts will be made to contact subjects who are lost to follow-up. These efforts must be documented in the subject's file.

The sponsor has the right to terminate the study at any time in case of SAEs or if special circumstances concerning the the company itself occur. In this event, the Investigator(s) will be informed of the reason for study termination.

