Study Design: This is a double-blind, multicenter, parallel group, vehicle-controlled long-term follow-up study to evaluate recurrence of AKs in subjects who completed study RD.06.SPR.112199. Only those subjects who achieved CR of treated AK lesions at the Final Visit (12 weeks after the last DL-PDT session) will be offered the opportunity to continue to be followed in the current study for 9 months to assess recurrence. After obtaining informed consent for this follow-up study, the subjects will return at Weeks 14 and 40, which correspond to 26 and 52 weeks after the last DL-PDT session, respectively to assess the lesions treated in the previous study for recurrence of AK. Recurrence will be determined by reappearance of those lesions completely cleared by 2 DL-PDT sessions, i.e., subjects whose lesions are evaluated to be non-CR at the visits in this study will be deemed to have recurrence. If the percentage of subjects maintaining complete response would be 60% at Visit 3 (52 weeks after the last DL-PDT), 40% of subjects would have experienced recurrence (subject recurrence response). The same calculation will be done for lesion complete response, to assess the lesion recurrence. There will be a telephone check-in with the subjects by the clinical site at Week 40 to help retain the subject's participation for the entire duration of the study. CCI

Number of Subjects:

Approximately 111 subjects from the MAL cream arm and 19 subjects from the vehicle cream arm from the previous study are expected to enroll in the follow-up study.

Treatment:

Neither investigational product nor intervention will be part of this study.

Study Duration:

The expected duration for each subject's participation in the study will be approximately 40 weeks from the completion of study RD.06.SPR.112199.

Study Population:

The study population will consist of adult male and female subjects with clinically confirmed mild to moderate actinic keratosis on the face and balding scalp, who have completed study RD.06.SPR.112199 with a Complete Response at Final Visit of that study, meaning those subjects, whose treated AKs were all cleared at 12 weeks after the last DL-PDT session.

Inclusion Criteria: To be eligible for study entry, subjects must satisfy all of the following inclusion criteria:

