8.5 Unscheduled Visit

The subject should be reminded to adhere to the study schedule. Unscheduled visits are defined as visits occurring outside of the visit window.

Assessments to be conducted at the unscheduled visit will depend on the reason for the visit and will be conducted at the discretion of the principal investigator. Any of the procedures/assessments listed in [Section 8.1.2](#) may be conducted, but not all are required.

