10.1.6 Handling of Missing Data

For the proportion of subjects with recurrence at 26 and 52 weeks after the last DL-PDT treatment, all subjects in the safety population with missing data will be classified as non-responders regardless of treatment allocation.

For the recurrence of cleared treated AK lesions at 26 and 52 weeks after the last DL-PDT treatment, missing counts of cleared treated AK lesions for subjects in the safety population will be imputed assuming that all baseline AK lesions had recurred regardless of treatment allocation.

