9.1.4. Analysis Visits Definition

Analysis visit will be calculated according to the following table (see Table 5) to summarize the data by proper visit.

Table 5 - Analysis Visits Definition

Clinical Visit	Analysis Visit	Analysis Visit Number	Target Study Day	Visit Window
Visit 1 (12 weeks after the last DL-PDT)	Week 14	11	Day of Visit 6 of study RD.06.SPR.112199	<= Target Study Day + 14 days
Visit 2 (26 weeks after the last DL-PDT)	Week 28	12	Day of last DL-PDT + 182 days	>= Target Study Day - 21 days <= Target Study Day + 21 days
Telephone Contact (38 weeks after the last DL-PDT)	Week 40	13	Day of last DL-PDT + 266 days	>= Target Study Day - 21 days <= Target Study Day + 21 days
Visit 3 (52 weeks after the last DL-PDT)	Week 54	14	Day of last DL-PDT + 364 days	>= Target Study Day - 28 days

Early termination visit will be managed as a stand-alone visit. The assessments performed at early termination visit will be windowed based on the analysis visit windows.

Unscheduled visits will be windowed based on the analysis visit windows.

If multiple assessments are performed within the same window, all assessments will be listed and the ones taken closest to the target study day will be used for the analysis.

This document is confidential.

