9.3. Protocol Deviations

Potential major protocol deviations may include but are not limited to:

- Eligibility deviations (inclusion/exclusion criteria);
- Noncompliance with study procedures if the consequence of noncompliance would compromise either the subject's safety and/or the study integrity, primary endpoint, and/or is not in line with Good Clinical Practice (GCP)/ICH guidelines;
- Use of prohibited concomitant therapies;
- Administrative error:
 - Accidental unblinding;
 - AK lesion counts and evaluation performed by a non-approved evaluator.

Major protocol deviations and major protocol deviations due to COVID-19 will be summarized using frequency and percentage (n, %) for each deviation coded term by treatment group and overall using the Safety Population. All protocol deviations will be listed.

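### Section 8.3.4 allows subjects to be discontinued from a follow-up-only study for schedule non-compliance or non-permitted therapy, and a 52-week status lost this way is counted as recurrence

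*Protocol*

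**What the plan says.** **No treatment.** The protocol synopsis states: "Neither investigational product nor intervention will be part of this study".

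**Discontinuation.** Protocol 8.3.4 lists "NON-COMPLIANCE WITH STUDY SCHEDULE" as a reason, with nothing attached to it. Under protocol violation it lists "Use of non-permitted concurrent therapy (unless discussed and agreed upon with the Investigator and medical monitor". It adds: "Investigators or the Sponsor can also withdraw subjects from the clinical study if deemed to be necessary". Data up to removal are kept. A final or early-termination (ET) visit is encouraged in 8.3.4, and 8.4.1 says that it should take place. Section 8.3.7 has the medical monitor notified when prohibited therapy is used, discusses how the subject may continue, and names early termination only as a possible outcome.

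**Missing data.** Under Protocol 10.1.6, "all subjects in the safety population with missing data will be classified as non-responders regardless of treatment allocation". Section 9.1.1 equates a non-complete responder with a subject recurrence. Imputed and observed-case summaries are both planned. No sensitivity analysis is planned.

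**Timing.** Protocol Table 1 allows ±5 days for Visit 3. Protocol 8.5 says: "Unscheduled visits are defined as visits occurring outside of the visit window". SAP Table 5 (Section 9.1.4) takes Visit 3 as ">= Target Study Day - 28 days", with a target of 364 days after the last DL-PDT and no upper limit shown. It assigns ET and unscheduled visits to the same analysis windows.

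**Deviations.** SAP 9.3 lists "Use of prohibited concomitant therapies", and certain procedural non-compliance, as potential major deviations to be tabulated in the Safety population.

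**The concern.** In a treatment trial, a removal rule may protect the subject from further dosing. Here there is no dosing, and follow-up to 52 weeks is what the study exists to obtain. Discontinuing a subject for a mistimed visit, or for using another therapy, gives up an outcome that could often still have been examined.

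The loss affects both planned summaries. The imputed one counts the subject as a recurrence whatever the reason for the missing value. The observed-case one leaves the subject out, and if removal followed treatment of a recurrence, it understates recurrence. With no sensitivity analysis planned, nothing else addresses the gap. Scheduled collection of adverse events, which serves the secondary objective, also ends early.

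The analysis does not need these removals, because SAP 9.3 tabulates such events as deviations in subjects who remain in the Safety population. The protocol already applies that logic to pregnancy: 9.2.1.4 keeps the subject in follow-up and notes that no intervention is given.

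**Working it through.** **Inputs.** 111 MAL and 19 vehicle subjects expected (synopsis); about 100 MAL completers (8.2.1); 40% recurrence, which is the synopsis's worked example and not a design assumption; visit windows from Protocol Table 1 and SAP Table 5.

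**1. The plan's own figure.** Going from 111 to about 100 completers implies 1 − 100/111 = 9.9% loss, or about 11 MAL subjects. This agrees with an assumed 10% loss: 100/0.90 = 111.1. The visible text states no dropout rate, and part of the sample-size section is redacted.

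**2. When removal loses the Week 54 value.** Week 54 starts at 364 − 28 = day 336 after the last DL-PDT. The Week 28 window is 182 ± 21, that is days 161 to 203. An ET examination before day 336 therefore cannot supply Week 54, and neither document provides for a later return.

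**3. Effect on the imputed rate.** With N enrolled, m missing at Week 54 and recurrence rate r among those observed, the imputed rate is [r(N − m) + m]/N and the shift is (1 − r)m/N.

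- MAL, r = 40%, m = 11: (0.4 × 100 + 11)/111 = 51/111 = 45.9%, a shift of 5.9 points.
- MAL, m = 3, 5 or 8: 41.6%, 42.7% or 44.3%.
- MAL, m = 11 at other rates: r = 20% gives 27.9%; r = 60% gives 64.0%.
- Average shift per missing subject at r = 40%: 0.6/111 = 0.54 points in MAL and 0.6/19 = 3.2 points in vehicle.
- Vehicle, m = 2: (0.4 × 17 + 2)/19 = 46.3%.

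**4. The avoidable part.** Assume that retained subjects would also recur at 40%. If none of the 11 losses comes from these two reasons, nothing is avoidable. If half do, the imputed rate falls from 45.9% to (0.4 × 105.5 + 5.5)/111 = 43.0%. If all do, it falls to 40.0%. The documents do not say which applies, so the range is 0 to 5.9 points.

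**5. The timing passages side by side.**

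- Protocol Table 1 puts Visit 3 at 52 weeks ± 5 days: 364 ± 5 = days 359 to 369 after the last DL-PDT.
- Table 1 also lets Visit 6 of the parent study, which is Visit 1 here, fall up to 28 days late: 84 + 28 = day 112.
- The synopsis describes about 40 weeks from completion of the parent study: 112 + 280 = day 392, which is 392 − 369 = 23 days past the window.
- Section 8.1 equates Week 40 with 52 weeks after the last DL-PDT. For this subject both cannot hold.
- SAP Table 5 would accept day 392.

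A subject who is punctual by one protocol clock is thus outside the schedule by the other, at a time that the analysis accepts.

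**The case against.** The case on the other side is substantial.

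- **The list permits and does not require.** Section 8.3.4 says that subjects can be withdrawn. Where the protocol requires withdrawal it says so, as in 8.3.6 when the investigator breaks the blind. A reader might infer that a visit outside ±5 days triggers removal, but no text says this.
- **Prohibited therapy has safeguards.** Section 8.3.4 carries an exception by agreement and 8.3.7 gives a route to continue. The point is therefore weaker there than for schedule non-compliance, which has neither.
- **A late Visit 3 is not lost in itself.** Out-of-window visits become unscheduled visits at which the listed assessments may be done, and the SAP window has no upper limit. Data are lost only if the subject is removed or not seen.
- **There are mitigations.** These are the final or ET assessments (which count as Week 54 from day 336), a retention call, the observed-case summary, and disposition by reason and arm (SAP 9.2.1). Safety information does not stop entirely either: related adverse events are followed until resolved or stable.
- **Some Table 2 agents might seem irrelevant to recurrence.** The documents do not support this. Section 8.3.7 prohibits these therapies because they may interfere with lesion assessment.
- **Retention alone could bias the endpoint.** If a recurred lesion is treated and looks clear at Visit 3, Section 9.1.1 would score it as a complete response.
- **The shift is modest against precision.** At 40% and n = 111, the 95% half-width is 1.96 × √(0.4 × 0.6/111), about 9 points, in a study with no hypothesis test.

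These arguments limit the size and scope of the point. They do not remove the gap: an unqualified reason to stop follow-up, no return at 52 weeks, and a missing value scored as recurrence. The bias argument shows that the SAP needs a rule for readings after therapy.

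**Conclusion.** The point holds as a weakness in wording that allows avoidable missing data in the primary endpoint. It is strongest for schedule non-compliance. For prohibited therapy, what remains is to align 8.3.4 with 8.3.7 and to supply the missing analysis rule.

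For MAL, the avoidable shift in the imputed rate is 0 to 5.9 points. This assumes the illustrative 40% recurrence, about 11 losses, and the same recurrence rate in subjects who would have been retained. A reader might attribute the whole move from 40.0% to 45.9% to Section 8.3.4. The documents do not support that, because the 11 are losses from all causes. Likewise, each removal adds 1/111 = 0.9 points (MAL) or 1/19 = 5.3 points (vehicle) only if that subject would have stayed clear. The averages of 0.54 and 3.2 points are the fairer figures.

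The change is worth making because it is cheap, and because one vehicle subject moves that arm's rate noticeably.

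**What to change.** 1. **Protocol 8.3.4.** State that a schedule deviation alone is recorded as a protocol deviation and does not end follow-up. State that the 52-week lesion and adverse-event assessment is still sought, even if late, for any subject who has not withdrawn consent. Leave the other withdrawal reasons, and the unblinding rule in 8.3.6, as they are.
2. **Visit timing.** Reconcile the synopsis, 8.1 and Table 1 with SAP Table 5 by counting Visit 2, the telephone call and Visit 3 from the last DL-PDT. The endpoint definition and the SAP already use that anchor.
3. **Prohibited therapy.** Leave the clinical rules of 8.3.7 unchanged. Reconcile 8.3.4 with them so that use of such therapy does not by itself end data collection.
4. **SAP.** Prespecify how a Visit 3 reading after lesion-directed therapy is classified, so that a treated recurrence is not scored as a maintained complete response.

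The cost is a short protocol and SAP amendment and a few more deviations to list. The examinations are already planned. The downside is that some Visit 3 examinations will be late or will follow other therapy, and these must be flagged.
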